### **Randomization**

Participants will be randomized to start with the control or *smart snack* condition in 1:1 ratio using blocks of size 4 to 6 to ensure balance over the entire sample. Blinding of participants and study staff is not feasible; some analyses may be conducted under blinding.

Participants will be given a study Apple iPhone, and if not already using for personal use, a Dexcom G6 transmitter and sensor to use during the study, as well as an Apple Watch that will be paired with the study iPhone, and a study scale. All study devices, including a urine pregnancy test if applicable will be given to the participant during this visit or delivered via courier.

### **Control arm (4 weeks)**

There will be a visit at the start of the control arm that will be held virtually using WebEx. This visit can be held in clinic. The purpose of this visit is to have the participants learn how to use study devices and the Dexcom app. Using the Webex platform, study staff can connect virtually

with participants for training on the devices and study procedures while they are at home. Participants will be trained in how to use the Dexcom G6 CGM system for those not already using the Dexcom G6 system including insertion, sensor change, and calibration. For participants who are current users of Dexcom G6 CGM system, the insertion, change, and calibration of the Dexcom G6 CGM device will not be discussed during this meeting. Participants will be trained in how to pair the Dexcom G6 transmitter to the Dexcom app on a provided study smart phone, to start and stop a new sensor session, and how to enter calibrations. The CGM alerts will be set at 70 mg/dL and 250 mg/dL. For participants with history of severe hypoglycemia requiring third party assistance, low glucose alerts will be conservatively set to 85 mg/dL. Participants can modify these settings. Participants will be instructed to manage their glucose as they normally do. For those participants with history of severe hypoglycemia requiring third party assistance, a participant's companion (who lives in the same house and is trained in the administration of glucagon as per study inclusion criteria) will be linked to the participant's Dexcom app. The Apple Watch will be paired with the Apple iPhone by the study staff before giving them to participants. Participants will be trained in how to use the Apple Watch, which will be used during the study to collect sleep data. This visit will take approximately 0.5 - 1.5 hours, depending on the subject's experience.

At the beginning of the control period, participants will record their weight using a scale provided by the study staff. During the 4-week control period, participants will wear Dexcom G6 CGM and the study Apple Watch. The Apple Watch will be used to track sleep metrics; therefore, participants are asked to wear the smart watch overnight and charge it during the day.

The goal of this control period is to gather CGM glucose data to assess baseline time in overnight hypoglycemia (<70 mg/dL and <54 mg/dL) and other glucose control metrics (mean glucose, % time in range 70-180 mg/dL, % time below range, % time above range) and evaluate the accuracy of the overnight low glucose prediction algorithm.

Participants will weigh themselves weekly in the morning after urinating and before eating their first meal and to record their weight to track baseline weight changes. Participants will also answer a one-item sleep quality survey weekly. Participants will be contacted weekly by study staff to collect weight measurements and responses to the sleep quality question.

There will be a closeout visit at the end of this arm that will last 10-15 minutes. This visit can be held virtually. Availability of Dexcom CGM data will be confirmed by the study staff and the participant will be asked about adverse events and medication changes. Participants that will use their own Dexcom G6 will share their Dexcom Clarity data with the clinic at this visit.

### **DailyDose + *smart snack* intervention arm (4 weeks)**

There will be a visit at the start of the intervention arm that will be held at OHSU's Biomedical Engineering Artificial Intelligence for Medical Systems (AIMS) Laboratory, the Harold Schnitzer Diabetes Health Center, or virtually using WebEx. A urine pregnancy test might be required for individuals of childbearing potential if the last pregnancy test was more than 7 days prior. This test must be negative before further participation is allowed. During this session, participants will go through the onboarding process with the DailyDose app. This process will occur with the study staff and involve:

- Training on using the Dexcom G6 CGM within the DailyDose app
- Setting up low and high blood glucose CGM-based alerts

- Setting up bedtime for running nocturnal low glucose prediction and receiving bedtime snack recommendation when applicable
- Review *smart snack* options that will be recommended by DailyDose and provided to participants during the intervention period (study protocol, Table 1) as well as present accessible snack alternatives (e.g., those already documented in the study protocol Table 2), in case participants has any allergies or food aversion related to DailyDose *smart snack* options. The study staff will also provide a card with bedtime snack options and replacements so that participants can easily find adequate alternatives to the snacks recommended by DailyDose (study protocol, Appendix F).
- Training on usage of the DailyDose app including how to setup alerts, predict likelihood of nocturnal low glucose, accept/decline *smart snack* recommendations, and use of the insights tab / settings / logbook features
- Training on usage of the Apple Watch

DailyDose has glucose alerts for safety. The Dexcom G6 CGM alerts in DailyDose will be set at 70 mg/dL and 250 mg/dL with user able to adjust. For participants with history of severe hypoglycemia requiring third party assistance, low glucose alerts will be conservatively set to 85 mg/dL. There is a very low glucose alert (glucose <55 mg/dL) that cannot be adjusted.

This visit will take approximately 2-3 hours, depending on the subject's experience.

Participants will go home and use the nocturnal low glucose alert feature of the DailyDose system for the next four weeks. Study staff may contact participants via text message or phone call at other times at the investigator's discretion. At the beginning of the intervention period, participants will record their weight using the scale provided by the study staff. Participants will wear Dexcom G6 CGM and the study Apple Watch. The Apple Watch will be used to track sleep metrics. Participants will use DailyDose and an AI-based prediction model to predict at bedtime the likelihood and time of the minimum overnight glucose. A *smart snack* recommendation will be given if there is a probability of overnight glucose drop below 70 mg/dL. The recommended bedtime treatment will have a carbohydrate content between 15 or 30 g depending on the predicted glucose drop, and a glycemic index defined by the estimated time of the predicted hypoglycemia event. If nocturnal hypoglycemia (glucose < 70 mg/dL) is predicted to occur 4 hours after bedtime, the recommended snack will have a balance of carbohydrate with higher amounts of protein or fat content. Several snack options will be provided to participants, so that there is more uniformity across participants (see Table 1). Participants will be instructed to manage their glucose as they normally do with the addition of these *smart snack* recommendations. Participants will have the ability to accept or decline *smart snack* recommendations.

Table 2 shows nutritional content of the options for recommended snacks.

Smart snack options	Low glucose predicted 0-4 hours after bedtime	Low glucose predicted 4-8 hours after bedtime
----------------------------	--	--

[figure not shown]
Small		
		
Large		 x 2
		 x 2

Table 1. Smart snack options and recommended amounts based on overnight low glucose predictions. The *CLIF BUILDERS* protein bars are gluten free. The *Oats 'n Honey* bars might contain trace amounts of gluten.

Snack option	Quantity	Measure	Wgt (g)	Cals (kcal)	Prot (g)	Carb (g)	Fat (g)	TotFib (g)	Sugar (g)
SLOW ABSORPTION									
Granola bar, crunchy, oats and honey	1	Each	21	95	1.5	14.5	3.5	1	5.5
Protein bar, chocolate peanut butter, Builders	1	Each	68	290	20	29	11	--	17
Protein bar, chewy, peanut almond & dark chocolate	1	Each	40	200	10	15	12	--	6
Protein bar, chocolate, Builders	1	Each	68	280	20	31	9	--	17

Protein bar, vanilla almond, Builders	1	Each	68	290	20	29	11	--	16
QUICK ABSORPTION									
Juice drink, cranberry cocktail	4	Ounce- weight	113.4	53.83	0	13.46	0	0	13.46
Juice, orange	4	Ounce- weight	113.4	54.65	0	12.75	0	0	11.29

Table 2. Smart snack options with macro nutrient analysis.

Participants will weigh themselves weekly in the morning after urinating and before eating their first meal and to record their weight to track baseline weight changes. Participants will also answer a one-item sleep quality survey weekly. Participants will be contacted weekly by study staff to collect weight measurements and responses to the sleep quality question.

At the end of the intervention period, participants will complete hypoglycemia awareness, diabetes distress scale, hypoglycemia fear survey, and sleep quality questionnaires to compare results with the questionnaires completed during the screening session.

There will be a closeout visit at the end of this arm that will last about 30 minutes. This visit can be held virtually. Availability of Dexcom CGM data will be confirmed by the study staff and the participant will be asked about adverse events and medication changes.

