## Protocol summary

Participants will be randomized to either first use CGM only to manage glucose for four weeks (control arm, usual care) followed by four weeks of DailyDose App + bedtime *smart snack* intervention (intervention arm), or vice-versa. There will be a one- to four week washout period between arms. See Figure 1 for a diagram of the study flow.

During the control arm, participants will wear CGM and will manage their glucose as usual (current care). Participants will be asked to wear a smart watch overnight to collect sleep metrics, weigh themselves weekly in the morning before eating, and answer a one-item sleep quality scale survey weekly. We will collect CGM measurements during the control arm for evaluation of effect of intervention and assessment of the accuracy of low glucose prediction.

During the *smart snack* intervention arm, participants will use the DailyDose app when they are getting ready for bed. An AI-based model in DailyDose will predict the likelihood of overnight low glucose at bedtime every night and will recommend a personalized snack to help avoid nocturnal hypoglycemia. The nutritional content of the snack (carbohydrate, protein, fat, etc.) will be dependent on the predicted overnight minimum glucose and the predicted time of the minimum overnight glucose level. During this arm, participants will also be asked to wear a smart watch overnight, weigh themselves weekly, and answer a one-item sleep quality scale survey weekly.

[figure not shown]

Figure 1. Study flow diagram

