Individuals of child-bearing potential will take a urine pregnancy test (UPT), which must be negative to participate. A venous blood sample will be taken for the following tests: hemoglobin A1C, complete blood count, complete metabolic set (including creatinine, liver set, and electrolytes) and thyroid-stimulating hormone (TSH). Blood draw labs and urine pregnancy testing will be completed within 1 week of screening at an OHSU outpatient phlebotomy lab. If a participant had any of these labs drawn with in the last 6 months and results are available for review within Epic or CareEverywhere for the study investigator to review, then those labs do not need to be drawn at this point.

A study investigator will assess inclusion/exclusion criteria and may review the participant's medical record for clarification as needed. The participant's glucose sensor data will be downloaded at the time of the screening visit or accessed online to confirm that the participant has experienced nocturnal hypoglycemia (i.e., two events) in the 30 days prior to the screening visit. A three-digit participant ID number will be assigned to the participant. Participants will complete hypoglycemia awareness, diabetes distress scale, hypoglycemia fear survey, and sleep quality questionnaires that will serve as a baseline to compare against results obtained at the end of the intervention period.

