due to technical problems, the participant may be asked if they can complete additional time in study with the goal to collect at least 2 weeks worth of data in at least one of the arms of the study, such that the participant can be included in the statistical analysis. Additional compensation will be provided for additional time in study. Problems that would qualify for extending the study time are 1) insufficient study supplies requiring the participant to go off of DailyDose + smart snack intervention or to discontinue the control arm for a period of time (such as running out of CGM supplies or bedtime snacks), 2) issues with the smartphone such that DailyDose cannot be used/accessed (such as a due to a damaged phone or problems with the internet connection that prevent data from being uploaded to the remote monitoring system), 3) issues with the CGM system or the capture of the CGM data during the control period or during the intervention period such that DailyDose cannot generate bedtime recommendations due to insufficient CGM data, or 4) scheduling issues such that the participant is unable to complete the control or the DailyDose + smart snack intervention period continuosly. Participants can complete up to 4 additional weeks to make up time the study was paused for technical reasons. Repeating the study time will be optional. The study team will track when participants extend their study time and the reason and this will be included in the annual report to the FDA.

Table 3: Schedule of Events

 DailyDose abbreviated Dd

 Randomization order abbreviations Control first (CG) Intervention first (IG)

 (CG) only

(IG) only

Collect demographic and other baseline characteristics	X											
UPT if applicable and not done in last 7 days (Point of care)	X	X						X				
Collect blood sample for HbA1c, CBC, CMP, TSH testing	X											
Collect information about medical history	X											
Collect information about concomitant medications	X	X	X	X	X	X	X	X	X	X	X	
Download participant's glucose sensor	X											
Complete 3 surveys	X					X 					X 	
Randomization		X										
Collect data on Adverse Events		X	X	X	X	X	X	X	X	X	X	
Train participants on the study procedures to do at home		X					X					
Train participants on use of Dexcom G6 CGM system with G6 and Clarity apps		X 					X 					
Train participants on use of Apple Watch		X										

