Collect sleep quality survey response			X	X	X	X		X	X	X	X	

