**Appendix D: Sleep quality Scale[24]****INSTRUCTIONS:**

- *The following question refers to your overall sleep quality for the **majority** of nights in the **past 7 days ONLY**.*
- *Please think about the quality of your sleep **overall**, such as how many hours of sleep you got, how easily you fell asleep, how often you woke up during the night (except to go to the bathroom), how often you woke up earlier than you had to in the morning, and how refreshing your sleep was.*

1. During the **past 7 days**, how would you rate your sleep quality overall?  
(Please mark only **1** box)

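### Sleep quality is scored weekly in both conditions, but the only comparison stated for it is end of intervention against screening; comparing the conditions would be a minor improvement needing no new data

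*Combined protocol and SAP*

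**What the plan says.** **Collection.** The Protocol summary asks participants in each arm to "answer a one-item sleep quality scale survey weekly". The Control arm section repeats this: "Participants will also answer a one-item sleep quality survey weekly". The intervention arm section adds: "Participants will be contacted weekly by study staff to collect weight measurements and responses to the sleep quality question". Appendix D holds the only sleep instrument in the protocol, a single item with 7-day recall that asks "how would you rate your sleep quality overall".

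**Comparison.** The Screening session section lists four questionnaires (hypoglycemia awareness, diabetes distress, hypoglycemia fear and sleep quality), ending with "sleep quality questionnaires that will serve as a baseline to compare against results obtained at the end of the intervention period". The intervention arm section closes with the same four, including "sleep quality questionnaires to compare results with the questionnaires completed during the screening session". No other sleep comparison is stated.

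**Analysis.** The Statistical analysis methods section opens with a general statement that the arms will be compared by a mixed model. Its lowest-level unit is a night or a 24-hour day, and weekly scores are not mentioned. Sleep quality is absent from the objectives and endpoints.

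**Schedule.** Table 3 has one row reading "Complete 3 surveys" and a separate row reading "Collect sleep quality survey response".

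**The concern.** A bedtime app and bedtime eating could plausibly help or disturb sleep, so readers will want to know which. The design can answer this with a randomised within-participant contrast, because the same item is scored in both conditions. The comparison actually stated has no concurrent control.

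Several things change between screening and the end of intervention whatever the condition. Time passes, participants receive a study phone and watch, and those not already using the study sensor switch to it. Entry also requires at least two overnight hypoglycemia episodes in the 30 days before screening. If such nights disturb sleep, the screening score may be worse than usual and improve without treatment. A before-after change can credit all of this to the snack intervention, or hide a real effect behind it.

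The protocol treats weight differently. It is collected at the same weekly contact, and its secondary endpoint covers both the intervention and the control period.

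**Working it through.** **Inputs from the documents.** 20 participants (Power analysis), allocated 1:1 (Randomization). Screening up to 12 weeks before the first arm (Screening session). Two arms of 4 weeks and a washout of 1 to 4 weeks (Protocol summary; Washout period). Weekly sleep scores, so 4 per condition.

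**Assumed inputs.** Weekly error SD = 1. Within-person SD shared by all scores in one period, τ = 0, 0.5 or 1. The documents give no SD or drift for sleep. They also state no figure for sleep that could be reproduced; the power statement concerns the primary endpoint only.

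**1. Data used.** The stated comparison uses one end-of-intervention score and one screening score. It uses none of the 4 control scores.

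**2. Interval from screening to end of intervention, before any make-up time.**
- Intervention first: 0 + 4 = 4 to 12 + 4 = 16 weeks.
- Control first: 0 + 4 + 1 + 4 = 9 to 12 + 4 + 4 + 4 = 24 weeks.
- At the same screening lead, the sequences differ by 5 to 8 weeks (control arm plus washout).

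**3. Precision, 20 participants.** Before-after, one score each: SE = √[2(τ² + 1)/20]. Crossover, mean of 4 scores per condition: SE = √[2(τ² + 1/4)/20].

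| τ | Before-after SE | Crossover SE | Ratio |
|---|---|---|---|
| 0 | 0.316 | 0.158 | 2.0 |
| 0.5 | 0.354 | 0.224 | 1.58 |
| 1.0 | 0.447 | 0.354 | 1.26 |

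**4. Effect of a change unrelated to treatment.** Let d be a shift since screening, in units of the within-person SD of a single score. The SE of the mean change is √(2/20) = 0.316. With no treatment effect, the two-sided 5% before-after test is significant with probability Φ(d/0.316 − 1.96) + Φ(−d/0.316 − 1.96):
- d = 0: 5%
- d = 0.25: 12%
- d = 0.50: 35%
- d = 0.75: 66%

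A period-adjusted crossover contrast with a correct error term stays near 5% for a shift common to both sequences.

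For linear drift, take the washout at its midpoint of 2.5 weeks and a screening lead of L weeks. The mean interval is [(L + 4) + (L + 10.5)]/2 = L + 7.25, which is 7.25 to 19.25 weeks. A drift of 0.02 per week biases the before-after change by 0.15 to 0.39; a drift of 0.05 biases it by 0.36 to 0.96.

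**5. Which crossover model.** Applying the planned model with only a random participant intercept to weekly scores is not safe. Within a participant, 8 scores leave 7 degrees of freedom: 6 carry weekly error (variance 1) and 1 carries the between-period difference (1 + 4τ²). The pooled residual variance is about (6 + 1 + 4τ²)/7 = 1 + 4τ²/7, so the model SE is about √[2(1 + 4τ²/7)/(4 × 20)].
- τ = 0.5: model SE 0.169 against a true 0.224. False-positive rate 2Φ(−1.96 × 0.169/0.224), about 14%.
- τ = 1: model SE 0.198 against a true 0.354. Rate about 27%.

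Simulation agrees: about 5%, 14% and 29% at τ = 0, 0.5 and 1. A period-adjusted comparison of participants' period means stayed at 5 to 6%.

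**6. Schedule.** The three-survey row is marked in column 1 (screening), column 6 (intervention-first only) and column 11 (control-first only). The sleep row is marked in columns 3 to 6 and 8 to 11, and column 1 is blank. The sleep row is already marked in columns 6 and 11, so counting sleep among the three surveys would enter it twice there.

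**The case against.** The strongest reply is that sleep quality is neither an objective nor an endpoint, and no hypothesis or power claim rests on it. This stands, and it limits the point to a minor one.

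A reader might infer that the plan discards the randomised comparison in favour of the uncontrolled one. The documents do not support that. The Statistical analysis methods section opens with a general commitment to compare arms and excludes nothing. The gap is that it specifies no analysis for weekly scores, while two other sections do name a comparison, with screening.

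A reader might also infer from Table 3 that no screening score will exist. That is too strong as well. The Screening session text plans it, the three surveys are not named, and the copy read here lacks the table's column headings. What stands is that four questionnaires in the text and three in the table need reconciling.

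Halving the standard error is the best case, since it needs fully independent weekly scores. Nor does randomisation remove expectation effects from a self-reported item in an open-label trial. Watch-based sleep metrics are collected in both conditions too, but no analysis of them is specified, so they do not fill the gap.

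**Conclusion.** The point holds as a minor improvement. The stated sleep comparison has no concurrent control, and its interval depends on the randomised sequence, so it cannot separate an intervention effect from time and study participation. Data for a comparison between conditions are already being collected.

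The before-after SE is about 1.3 to 2 times the crossover SE, and a shift of half a within-person SD unrelated to treatment would give a false finding in about 35% of trials. These sizes rest on assumed variances and shifts. The direction does not depend on the assumed τ: with equal variances at each occasion, averaging four scores per condition always gives the smaller SE. The primary conclusion is unaffected. The calculation also assumes that the questionnaire at screening and at end of intervention is the Appendix D item.

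**What to change.** - **Statistical analysis methods:** state that sleep quality is compared between intervention and control using each participant's mean weekly score per period, adjusted for period and sequence. A mixed model on weekly scores is an alternative if it includes a participant-by-period random term; a random participant intercept alone is not enough.
- **Screening session and intervention arm sections:** keep the screening comparison for sleep if wanted, labelled as descriptive only.
- **Table 3:** reconcile the three surveys and the separate sleep row with the four questionnaires named at screening, and show whether the sleep item is completed at that visit.
- **Reporting:** note that the item is self-reported and open-label.

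The cost is a few sentences of wording and one extra model, with no new visits, data or participants. The remedy is specific to sleep: the other three questionnaires are completed only at screening and end of intervention, so they have no control-period scores to compare.
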